## **BACKGROUND**

Preterm premature rupture of the membranes (PPROM) is defined as spontaneous rupture of the membranes before labor at less than 37 weeks of gestation. It complicates 3 percent of pregnancies but is responsible for one third of cases of preterm birth, which is the leading cause of perinatal morbidity and mortality in developed countries. PPROM etiology is still unclear but underlying infectious process, increased inflammatory pathway activation and genetic predisposition are probably involved. Latency time from PPROM to delivery is usually brief and inversely proportional to gestational age (GA) at rupture. During this time, intrauterine infection, placental abruption, umbilical cord compression or prolapse, and fetal compression and hypoxia are possible consequences. Chorioamnionitis is the major maternal consequence of PPROM. Neonatal morbidity is also higher when PPROM is complicated by chorioamnionitis but prematurity remains the major neonatal consequence after PPROM. Several studies support that prolonged latency improves fetal maturation and does not worsen neonatal prognosis, for a given GA at birth. In order to increase GA at birth, expectant management of viable pregnancies with prophylactic antibiotic administration is recommended. Antepartum bed rest is also widely prescribed, although its effectiveness to prevent preterm birth has not been demonstrated.

## **OBJETIVE**

We aimed to access the impact of bed rest in latency time to delivery, chorioamnionitis incidence and other maternal and neonatal outcomes in pregnancies complicated by PPROM, thus enabling proper sample size calculation for future powered randomized controlled trial.

## **STUDY DESIGN**

Pilot unblinded randomized controlled trial (1:1 allocation ratio).

Simple random allocation sequence generated by the investigators and implemented by sequentially numbered sealed envelopes.

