## **POPULATION**

Eligible patients include those with single pregnancies with PPROM at  $24^{+0}$ - $33^{+6}$  weeks of gestation admitted to our tertiary center.

PPROM diagnosis on the basis of patient's history and sterile speculum examination with visualization of amniotic fluid pooling in the vagina and/or leaking from the cervical canal.

Exclusion criteria: indication for immediate delivery on admission (chorioamnionitis, placenta abruption, cord prolapse, signs of fetal hypoxia/distress), fetal malformations, multiple gestation, and maternal immunosuppressive disease.

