## **SAMPLE SIZE**

Considering future sample size calculation based upon assumed differences between groups regarding latency and infection, we aim a sample of 30 participants.

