## **ENROLLEMENT**

Participants enrolled by physicians after hospital admission and after written informed consent is obtained.

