## **STATISTICAL ANALYSES**

Intention-to-treat analysis; significance level of 5%.

Statistical analysis performed by IBM® SPSS® Statistics version 24.

Categorical variables compared by Chi-square or Fisher exact test as appropriate. Medians of quantitative variables compared by Mann-Whitney U test. Latency from PPROM to delivery compared by univariate analysis using Mann-Whitney U test and by survival analysis using Kaplan-Meier curve with group stratification.

Sample size for future RCT calculated based on difference between the means of latency time.

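### The investigators generate the allocation list, and nothing in the plan separates them from the physicians who enrol; independent list-keeping is a cheap improvement

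*Combined protocol and SAP*

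**What the plan says.** All references are to the combined protocol and SAP.

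- **Generation and implementation (STUDY DESIGN):** "Simple random allocation sequence generated by the investigators and implemented by sequentially numbered sealed envelopes". The same section describes the trial as a pilot, unblinded, with 1:1 allocation.
- **Setting (CENTER, POPULATION):** one obstetric department, recruiting women "admitted to our tertiary center".
- **Enrolment (ENROLLEMENT):** "Participants enrolled by physicians after hospital admission and after written informed consent is obtained".
- **Size (SAMPLE SIZE):** "we aim a sample of 30 participants".
- **Use of the result (STATISTICAL ANALYSES):** analysis by intention to treat at the 5% level, with latency compared by Mann-Whitney and Kaplan-Meier, and "Sample size for future RCT calculated based on difference between the means of latency time".

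The documents do not say whether the list-making investigators also enrol, or who prepares, holds or opens the envelopes. Nor do they say whether the envelopes are opaque, or at what moment one is opened.

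**The concern.** Sealed envelopes hide the next assignment only from people who have not seen the list. The plan gives the making of that list to the study team itself, in a single department whose physicians recruit the women, and it states no separation of the two tasks. If the roles overlap, an enroller could know the next arm before deciding whether, or when, to approach a woman.

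The enroller would also have something to act on. BACKGROUND says that latency falls as gestational age at rupture rises. POPULATION admits women from 24+0 to 33+6 weeks, and INTERVENTION plans delivery for the 34th week. Taking that as 34+0, the longest planned latency is 70 days for a woman who ruptures at 24+0 and 1 day for one at 33+6. Gestational age is known before enrolment. BACKGROUND also says that bed rest is in common use, so clinicians may hold a preference.

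What is at stake is the latency difference. It is tested at 5% and, more importantly for a pilot, it feeds the sample size of the next trial. Intention-to-treat analysis keeps the groups as enrolled, including any imbalance created before enrolment, and the planned latency comparisons do not adjust for gestational age.

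**Working it through.** **No plan figure to reproduce.** The only design number is 30, given without effect size, SD or power, and it is not disputed here. What follows is an illustration.

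**1. Routes to foreknowledge**
- *Past allocations:* closed. Under simple 1:1 randomisation a guess at the next arm is right 50% of the time, whatever has gone before.
- *Lack of blinding:* by itself this gives no foreknowledge when there are no blocks.
- *Seeing the list, or reading or opening an envelope early:* not closed by anything the plan states.

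**2. Size of the bias if the list is known**

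Inputs from the documents: 30 women in total, 1:1, 5% level. Assumed: two-sided test, 15 per arm (simple randomisation gives exactly 15/15 only 14.4% of the time), no true effect, and standard normal prognosis with correlation ρ to latency. A woman on the wrong side of average prognosis for the next arm is declined with probability q and replaced. Every enrolment is informed, and all steering goes one way.

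Among women enrolled to an arm, the share on the favoured side is 0.5/(1 − q/2). The mean of a half-normal is √(2/π) = 0.798. Hence

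shift between arms = 2 × 0.798 × ρ × q/(2 − q), in SD of latency.

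Example: ρ = 1, q = 0.25 gives 1.596 × 0.25/1.75 = 0.228.

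The standard error is √(2/15) = 0.365 SD. The approximate rejection rate is 1 − Φ(1.96 − shift/0.365) + Φ(−1.96 − shift/0.365). The last column is a t test in 20,000 simulated trials per row.

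| ρ | q | Shift (SD) | Rejection, formula | Rejection, simulated |
|---|---|---|---|---|
| 0.3 | 0.10 | 0.03 | 5.1% | 5.0% |
| 0.3 | 0.25 | 0.07 | 5.4% | 5.3% |
| 0.3 | 0.50 | 0.16 | 7.2% | 7.2% |
| 0.5 | 0.10 | 0.04 | 5.2% | 5.6% |
| 0.5 | 0.25 | 0.11 | 6.1% | 5.9% |
| 0.5 | 0.50 | 0.27 | 11.3% | 11.2% |
| 1 | 0.10 | 0.08 | 5.6% | 5.6% |
| 1 | 0.25 | 0.23 | 9.6% | 9.7% |
| 1 | 0.50 | 0.53 | 30.8% | 31.7% |

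Mann-Whitney, the plan's test, gave rates within 1.5 percentage points of these. With ρ = 0.5 and only half the enrolments informed, rejection is about 5% (q = 0.25) and 6% (q = 0.50).

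**3. Carry-over to the future trial**

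Assume a true effect of 0.5 SD (not in the documents), two-sided 5% and 80% power. Then n per arm = 2(1.960 + 0.842)²/d² = 15.70/d², which is 63 without bias. True power at a chosen n is Φ(0.5/√(2/n) − 1.96).

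| Bias (SD) | Apparent d | n per arm | True power |
|---|---|---|---|
| +0.11 | 0.61 | 43 | 64% |
| −0.11 | 0.39 | 104 | 95% |
| +0.23 | 0.73 | 30 | 49% |
| −0.23 | 0.27 | 216 | over 99% |

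**The case against.** The strongest reply is that the problem is inferred from silence. STUDY DESIGN says that investigators make the list and ENROLLEMENT says that physicians enrol. No section says that they are the same people or that enrollers can see the list. A reader might conclude that the plan, followed as written, hands the next assignment to the recruiting physician. The documents do not support that. They state who generates the sequence, and the rest is open. Nothing suggests misconduct.

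The plan also has real safeguards. Numbering and sealing are concealment measures. Unblocked randomisation removes prediction, so the open-label design is not itself a source of foreknowledge. Enrolment comes after written consent, although the plan does not say that the envelope is opened after it.

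The larger rejection rates are close to a worst case, since they need judged prognosis to equal the outcome and every enrolment to be informed and steered the same way. And in a pilot of 30 the sampling error of the difference (0.365 SD) exceeds most of the biases shown.

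What stands: none of these safeguards works against a person who has seen the list, and the plan places the list with the study team. Sampling error is visible in a confidence interval; selection bias is not, and it carries into the next trial's sample size.

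**Conclusion.** The point holds as a weakness in the stated allocation procedure, not as a demonstrated breach. List generation by the investigators is stated. Foreknowledge at enrolment is plausible in a single department but is not stated. Because the plan names a generator inside the study team, an independent one is a better method and not only a missing detail.

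The size cannot be fixed from the documents. If women whose prognosis does not match the next arm are declined 10% of the time, the effect is negligible. At 25–50% it is 0.07–0.16 SD (5–7% rejection) at correlation 0.3 and 0.11–0.27 SD (6–11%) at correlation 0.5. It reaches 0.23–0.53 SD (10–32%) only when prognosis equals outcome and all enrolments are informed. A reader might take the 32% as an estimate of this trial's type I error; it is the upper end of an illustration. The support for steering rests on gestational age, the one predictor of latency that the documents name. Grade: cheap improvement.

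**What to change.** In STUDY DESIGN, replace generation by the investigators with generation and custody of the list by an existing hospital person or office with no part in enrolling or treating participants (for example pharmacy or a statistics office), or with a free web randomisation tool.

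If envelopes stay, state that they are opaque and that each is opened in number order, only after consent and baseline data (including gestational age at rupture) are recorded and the woman's study number is written on it. Keep a log of openings. If enrolment has already begun, record who generated, held and had sight of the list, and report it.

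The cost is a sentence or two of protocol text and a small one-off coordination task for existing personnel. It needs no extra patients, visits or assessors, which suits a trial that reports no funding.

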## **CENTER**

Department of Obstetrics, Gynecology and Reproductive Medicine, CHLN - Hospital Universitário de Santa Maria, Lisboa, Portugal.

## **POPULATION**

Eligible patients include those with single pregnancies with PPROM at  $24^{+0}$ - $33^{+6}$  weeks of gestation admitted to our tertiary center.

PPROM diagnosis on the basis of patient's history and sterile speculum examination with visualization of amniotic fluid pooling in the vagina and/or leaking from the cervical canal.

Exclusion criteria: indication for immediate delivery on admission (chorioamnionitis, placenta abruption, cord prolapse, signs of fetal hypoxia/distress), fetal malformations, multiple gestation, and maternal immunosuppressive disease.

## **SAMPLE SIZE**

Considering future sample size calculation based upon assumed differences between groups regarding latency and infection, we aim a sample of 30 participants.

## **ENROLLEMENT**

Participants enrolled by physicians after hospital admission and after written informed consent is obtained.

## **INTERVENTION**

Bed rest vs activity: Activity restriction group with motion limited to bathroom privileges and walks to the ward canteen four times per day. Participants on complete bed rest group keep antepartum confinement to bed with toileting restricted to bedpan use. Participants in this group receive prophylactic subcutaneous enoxaparin (40mg/day).

All patients receive standard care for PPROM according to the institution protocol, including hospital admission, antibiotic prophylaxis (ampicillin IV 2mg/4id plus erythromycin IV 500m/4id for 48h, followed by amoxicillin PO 500 mg/3id plus erythromycin PO 500 mg/3id for 5 days), fetal lung maturation (betamethasone IM 12mg/d for 48h), leucogram and C reactive protein (CRP) analysis (daily for 1 week and thrice weekly after), nonstress tests daily, and weekly ultrasound assessment (biophysical profile and flowmetry).

Delivery is planned for 34th week. In case of spontaneous labor or adverse occurrence (chorioamnionitis, abruptio placentae, signs of fetal hypoxia/distress) it can occur earlier. Mode of delivery respected obstetrical indications.

## **OUTCOMES**

Maternal outcomes: latency to delivery after PPROM, clinical chorioamnionitis (defined as maternal fever plus leukocytosis and CRP elevation, or as maternal fever plus any two of the following: fetal tachycardia; maternal tachycardia; uterine tenderness; purulent amniotic fluid), cause of pregnancy termination (spontaneous labor, 34th week, adverse occurrence), mode of delivery, placenta abruption, cord prolapse, and thromboembolic events.

Neonatal outcomes: included GA at delivery, birth weight, APGAR score at fifth minute, length of hospitalization, neonatal sepsis, composite adverse pulmonary outcome (need for ventilatory support, respiratory distress syndrome, bronchopulmonary dysplasia), and neonatal death.

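### Should latency be timed from randomisation rather than from rupture of the membranes?

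*Combined protocol and SAP*

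**What the plan says.** The outcome is "Maternal outcomes: latency to delivery after PPROM". STATISTICAL ANALYSES uses the same origin: "Latency from PPROM to delivery compared by univariate analysis using Mann-Whitney U test", together with "survival analysis using Kaplan-Meier curve with group stratification". BACKGROUND also measures latency from rupture: "Latency time from PPROM to delivery is usually brief and inversely proportional to gestational age (GA) at rupture".

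Entry comes later: "Participants enrolled by physicians after hospital admission and after written informed consent is obtained" (ENROLLEMENT). The time between rupture and entry is neither stated nor limited, and no delayed-entry handling is described. The design is a "Pilot unblinded randomized controlled trial (1:1 allocation ratio", with 30 women planned, about 15 per arm, analysed by intention to treat. The figure carried forward is set out as "Sample size for future RCT calculated based on difference between the means of latency time".

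**The concern.** A woman has to be undelivered to be enrolled. The time from rupture to randomisation is therefore event-free by construction, and bed rest cannot have influenced it. The usual advice for a randomised time-to-event comparison is to start the clock at randomisation.

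Four things could be at stake:

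- a biased comparison, if this were true immortal time;
- an inflated SD feeding the future sample size;
- a chance imbalance in the delay between two arms of about 15;
- arm-level curves that understate early delivery.

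Because the plan itself calls latency usually brief, a delay of a day or more would be a visible share of it.

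**Working it through.** **Inputs.** From the documents: origin at rupture, entry after consent, 1:1 random allocation, about 15 per arm, 5% significance level (taken as two-sided), delivery planned for the 34th week. Assumed, because the documents are silent: mean latency m = 7 or 14 days and mean entry delay d = 0.5, 1 or 2 days, both exponential. The plan states no figure on this point that could be reproduced.

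**Bias.** Write T = D + R, with D from rupture to randomisation and R from randomisation to delivery. D is settled before allocation, so its expectation is the same in both arms and E(T | bed rest) − E(T | activity) = E(R | bed rest) − E(R | activity). In simulation with mean R of 10 and 20 days and mean D of 1 day, the mean difference was 10.0 days on either clock, or 5.8 days on either clock with a cap at 34 weeks.

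**Precision.** Var(T) = Var(R) + Var(D) + 2Cov(D, R). Under the exponential assumptions, D among enrolled women has mean e = md/(m + d) and is independent of R. Variance inflation is then (e/m)² = (d/(m + d))²:

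| m (days) | d = 0.5 | d = 1 | d = 2 |
|---|---|---|---|
| 7 | (0.5/7.5)² = 0.4% | (1/8)² = 1.6% | (2/9)² = 4.9% |
| 14 | (0.5/14.5)² = 0.1% | (1/15)² = 0.4% | (2/16)² = 1.6% |

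**Chance imbalance.** The SD of the difference in mean delay is e√(2/15): 0.17, 0.32 and 0.57 day at m = 7, and 0.18, 0.34 and 0.64 day at m = 14. The standard error of the latency difference is m√(2/15), that is 2.6 and 5.1 days. The squared ratio of the two is (e/m)², which is the inflation in the table. Imbalance and larger SD are therefore one cost, not two.

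**Test behaviour.** In 20,000 simulated trials per setting, the null Mann-Whitney rejection rate was 4.4% to 4.7% from either origin. With mean latency doubled in one arm, power was 32.9% to 33.4% from randomisation and 32.0% to 33.3% from rupture.

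**The planned delivery date.** The 34th-week plan caps latency and makes D and R negatively related: a woman who enters later has less time left. In the extreme where every woman reaches the planned date G days after rupture, R = G − D. With G independent of D, Var(R) = Var(G) + Var(D), which exceeds Var(T) = Var(G), so the randomisation clock is the noisier one. Under a range of assumed caps, the rupture-to-randomisation variance ratio ran from 1.06 down to 0.87. It falls below 1 only when the cap binds for many women. If ruptures are spread evenly over the eligible gestational weeks, it stays slightly above 1.

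**Arm-level description.** Delivery within 48 hours, measured from rupture in enrolled women, is 19.6%, 15.6% and 11.3% at m = 7, against 24.9% if every ruptured woman were counted. The matching medians are 5.3, 5.8 and 6.6 days against 4.9. That comparator includes women who deliver before they could be enrolled. POPULATION restricts eligibility to women admitted to the centre with no indication for immediate delivery, and delivery within 48 hours is not a listed outcome.

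**Would delayed entry help?** Root mean squared error of the arm median against that wider target, at 15 per arm (4,000 runs), ordinary versus delayed-entry Kaplan-Meier:

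| m (days) | d = 0.5 | d = 1 | d = 2 |
|---|---|---|---|
| 7 | 2.00 v 2.08 | 2.15 v 2.21 | 2.69 v 2.35 |
| 14 | 3.79 v 3.92 | 3.94 v 4.08 | 4.44 v 4.50 |

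Delayed entry does better in one setting of six.

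**The case for a change.** The strongest case for a change is that the delay is unknown and could be longer than assumed, while the pilot exists to supply planning figures. With mean R of 10 and 20 days and a mean delay of 5 days, the future size per arm for 80% power is 44 from rupture against 40 from randomisation. With the 34-week cap in that model it is 66 against 57. Mann-Whitney power at 15 per arm falls from 34.0% to 29.8%, or from 23.0% to 20.0% with the cap. Relative measures also move a little towards the null: the log-rank hazard ratio goes from 0.48 to 0.50 without the cap. Adding an analysis from randomisation would cost little.

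Part of this stands. A long and variable delay would cost something, and nothing in the documents rules it out. But a constant delay costs no precision, and at a mean of 1 day the same model gives 40 against 40, or 56 against 56 with the cap. The larger SD is also not an error: it is the correct SD for a future trial that keeps latency from rupture as its outcome, and an SD taken from randomisation would then understate that trial's size. The plan specifies no hazard ratio. Finally, the pilot's own noise is far larger: with 15 per arm and exponential latency, the pooled variance estimate ranges (95%) from about 66% below to about 130% above its true value.

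**Conclusion.** The observation is correct, but it calls for no change. Followed as written, the plan gives an unbiased mean difference, a test of the right size and a curve that accurately describes women still undelivered at enrolment. It does so on a definition of latency used consistently from BACKGROUND through STATISTICAL ANALYSES. For mean delays up to 2 days the cost is at most about 5% in variance and 1 percentage point of power in the uncapped model; if entry follows rupture within hours it is negligible (mean delay 2.4 hours, m = 7: 0.02% in variance).

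The absence of bias rests on random allocation and on the delay being fixed before it. The sizes rest on assumed delays and an assumed shape for latency, and the capped cases show that neither the size nor the direction of the precision effect is assured. Reporting the rupture-to-randomisation interval by arm would add useful detail, but the conclusions do not depend on it.

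### Enoxaparin is given in one arm only, yet apart from placental abruption no maternal bleeding outcome is recorded in either arm

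*Combined protocol and SAP*

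**What the plan says.** The arms differ by more than mobility. Of the complete bed rest group alone, the INTERVENTION section says: "Participants in this group receive prophylactic subcutaneous enoxaparin (40mg/day"). It gives no start, stop or peripartum timing for the drug. The same section states "Delivery is planned for 34" (the 34th week), and adds: "In case of spontaneous labor or adverse occurrence (chorioamnionitis, abruptio placentae, signs of fetal hypoxia/distress) it can occur earlier". The maternal blood tests it names are "leucogram and C reactive protein (CRP) analysis (daily for 1 week and thrice weekly after"); neither haemoglobin nor platelets are mentioned.

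Under OUTCOMES, the maternal list runs from latency, clinical chorioamnionitis and the cause of ending the pregnancy to "mode of delivery, placenta abruption, cord prolapse, and thromboembolic events". The neonatal list, which closes with "composite adverse pulmonary outcome (need for ventilatory support, respiratory distress syndrome, bronchopulmonary dysplasia), and neonatal death", has no bleeding item either. No observation window is given for the maternal events, and no section describes adverse-event reporting.

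The OBJETIVE section sets out to assess the "impact of bed rest in latency time to delivery, chorioamnionitis incidence and other maternal and neonatal outcomes". STATISTICAL ANALYSES specifies intention to treat, a 5% level and chi-square or Fisher tests for categorical variables. It bases the size of the future trial on the difference in mean latency.

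**The concern.** What is randomised is in practice a package: confinement to bed plus an anticoagulant, against activity without one. Bleeding is the foreseeable adverse effect of an anticoagulant. That is general pharmacology and not a statement in the document, but it is the reason to look for a bleeding item, and the outcome list has almost none. Unplanned delivery is possible in either arm, and nothing in the text rules out delivery soon after a dose.

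What is at stake is the maternal safety report. A finding of no thromboembolic events would be silent on bleeding, and a reader could take the bed rest package to be free of maternal cost when the relevant events had simply not been collected. The stated objective covers maternal outcomes beyond latency and infection, so this falls within what the pilot undertakes to describe.

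The missing window adds to the problem. Latency is the quantity being compared. If event counting stops at delivery, the arms may be observed for different lengths of time, and postpartum events of either kind drop out.

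**Working it through.** **1. Which events have a place in the plan.** This is settled by reading.

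| Maternal event | Listed under OUTCOMES? | Another route to record it? |
|---|---|---|
| Thromboembolism | Yes | Not needed |
| Placental abruption | Yes | Also an adverse occurrence that can bring delivery forward |
| Other antepartum or postpartum haemorrhage | No | None described |
| Transfusion | No | None described |
| Wound or injection-site haematoma | No | None described |

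The asymmetry in recording is confirmed, with abruption as the one bleeding-related exception.

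**2. Arm size.** SAMPLE SIZE says "we aim a sample of 30 participants". That figure cannot be re-derived, because no effect size, SD, event rate or power is given. STUDY DESIGN states 1:1 simple allocation, so the expected size is 30/2 = 15 per arm. An exact 15/15 split is not guaranteed: arm sizes fall between 10 and 20 with probability 95.7%.

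**3. Would there be anything to record?** The documents give no bleeding rate. Assume a total risk p of 3% to 10% around delivery. The chance of at least one event among 15 is 1 − (1 − p)^15:
- p = 3%: 1 − 0.97^15 = 36.7%
- p = 10%: 1 − 0.90^15 = 79.4%

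This is total bleeding, not an excess due to enoxaparin. The same p in the activity arm gives the same figures. The calculation shows only that bleeding could well occur and, unless it was abruption, would have no place in the outcomes.

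**4. What a recorded zero would say.** The one-sided 95% upper bound for 0 of n is 1 − 0.05^(1/n):
- n = 15: 18.1% (two-sided exact limit 1 − 0.025^(1/15) = 21.8%)
- n = 10: 25.9%
- n = 20: 13.9%

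**5. Could the arms be compared?** At 15 per arm, Fisher's test gives p = 0.0996 for 4 vs 0 events and p = 0.042 for 5 vs 0, so at least 5 vs 0 is needed. Exact power at the two-sided 5% level, with all rates assumed and two-sidedness also assumed because the plan does not state it:

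| Outcome | Assumed rates | Exact power, 15 vs 15 |
|---|---|---|
| Bleeding | 5% vs 15% | 3.0% |
| Bleeding | 5% vs 20% | 8.3% |
| Bleeding | 10% vs 30% | 14.9% |
| Thromboembolism | 1% vs 5% | 0.05% |
| Thromboembolism | 2% vs 10% | 1.0% |

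For the two thromboembolism rows, 80% power would take about 285 and 138 women per arm (normal approximation). Neither event can be compared usefully in 30 women; both can only be described.

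**The case against.** The strongest reply is that a bleeding item would buy little. A pilot of 30 cannot estimate a bleeding rate with useful precision or compare the arms, and STATISTICAL ANALYSES sizes the next trial on mean latency, into which no bleeding count enters. Both statements are correct, and it would be wrong to say that the count is needed to size the larger trial. Low power is not a reason to leave the item out, however. The plan already lists thromboembolism, cord prolapse and neonatal death, which 30 women are also poorly placed to compare.

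A second reply is that thromboembolism need not be a benefit measure at all. It can be read as a safety outcome for immobility, placed beside abruption and cord prolapse, and on that reading a harm of the bed rest arm is being recorded. This is a fair reading. Because bed rest and enoxaparin are given together, thromboembolism is not a clean measure of either. The gap in bleeding remains on both readings.

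A reader might infer more than the text supports:
- That the trial can see the benefit of the bed rest package but not its harm. Step 5 shows that it can demonstrate neither.
- That enoxaparin continues up to delivery. No stop time is stated, so this is inference. No view is taken here on dose or peripartum handling.
- That 37% to 79% is the chance of missing a drug harm. It is built on an assumed total risk.
- That platelet counts and a postpartum visit are already in place. The document names only a leucogram and CRP, and mentions no postpartum visit.
- That thromboembolism goes unrecorded after delivery. It is a named outcome and is not limited to the antenatal period; what is missing is a stated end point.

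**Conclusion.** The point holds as a gap in what is recorded. An anticoagulant is given in one arm only, thromboembolic events are an outcome, and apart from placental abruption no maternal bleeding outcome or general adverse-event collection is described. Followed as written, the trial cannot report bleeding by arm.

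The consequence is limited to maternal safety reporting. The latency and chorioamnionitis comparisons, the allocation and the future sample-size calculation are unaffected. The conclusion itself needs no event rate; only the illustrative 37% to 79% does, and it rests on an assumed 3% to 10% total risk and 15 women in the arm. The 18% bound rests on the arm size alone. The change is worth making because it is cheap and closes a foreseeable hole, not because 30 women could settle the question.

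**What to change.** Add one descriptive maternal bleeding outcome to OUTCOMES, for both arms, taken from the chart: antepartum or postpartum haemorrhage, transfusion, or wound or injection-site haematoma. Define each component in advance so that both arms are coded alike in an unblinded trial.

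Count bleeding and thromboembolic events from randomisation to the same fixed point after delivery in both arms, such as maternal hospital discharge or a stated number of days. Discharge is the cheaper choice; a stated number of days is cleaner, because length of stay may itself differ by arm. The antenatal part of the window will still vary with latency, so report time under observation alongside the counts.

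Report counts by allocated arm with exact confidence intervals, and state that no conclusion about a difference is intended. Leave platelets out unless the existing samples already report them.

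The cost is a few chart items for 30 women, plus a contact after discharge only if the chosen window runs beyond it. The downside is one more exploratory outcome with very low power. Sample size, allocation and the latency analysis do not change.
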